6. DATA MANAGEMENT

Aim 1:

Cervical cancer screening care cascade: The care cascade will examine the counts and proportions aggregated from the selected FP clinics as outlined in Figure 3. This cascade will account for appropriate exits from the cascade (e.g. outside screening age range, or screened negative) and losses in the cascade (e.g. not screened, or positive screen not referred for follow-up). Our research group has experience working with this type of complex care cascade in the setting of isoniazid prophylactic therapy for tuberculosis prevention, where there are multiple steps at which individuals can exit appropriately, be lost, or move on to the next step (55). We aim to model a cervical cancer screening care cascade in a similar manner.

Correlates of screening: Cervical cancer screening will be modeled as a binary outcome. Logistic regression will be used to examine correlates of screening including age, HIV status of clients, and specific clinic characteristics (detailed in Procedures). Analyses will be adjusted for any clustering by clinic.

Aim 2: The primary outcome is the proportion of all FP clients aged 21-65 years who were screened for cervical cancer over the total number of eligible clients. These outcomes will be assessed every 3 months in the 12-month study period. We are requesting an extension of the trial for an additional 6 months. Women who are not FP clients who are referred to a clinic solely for screening will be excluded as they could inflate the proportion of women screened. These women will be identified because they did not receive FP products or HIV testing and were only entered in the FP register because of screening. Generalized estimating equations with a binary link, clustered by clinic, will compare proportions screened in intervention versus control clinics longitudinally to account for correlation across time and between clinics. Interviews will be audio-recorded, transcribed, translated, coded for major themes, and analyzed using Dedoose software (56).

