C.1.E. Preliminary data on cervical cancer screening in Mombasa County from the FP HIV SAIA trial show low screening and incomplete documentation. [name] has had discussions with key collaborators in Mombasa County including the Director of Health (see letter), noting that the majority of cervical cancer screening is conducted in either FP clinics or HIV clinics. The County's policy is that screening should be documented in the FP register. Cervical cancer screening is reported to the County for all clinics that receive County FP commodities. These data are compiled into the District Health Information System (DHIS). The quality of different data sources has not been formally evaluated. Preliminary results from the cervical cancer screening review linked to the FP HIV SAIA trial underscore the importance of the project proposed in the present application. The 60 clinics analyzed saw a mean of 204 FP clients per clinic (SD 172) during a 3-month period (a total of 12,236 clients over the three-month period of our data review). Of the 60 clinics, 4 (7%) did not record cervical cancer screening in the FP register, but reported recording it elsewhere. Because we did not review these alternative records in this initial survey, these clinics are excluded from subsequent analyses. Of the 56 remaining clinics, 7 (13%) recorded any cervical cancer screening. Only 120 women (1%) were screened. These preliminary data suggest few FP clinics perform cervical cancer screening, and that most women accessing FP services are probably not being screened for cervical cancer. Of the clinics offering screening, not all are documenting this activity in the FP register. Moving forward, data collected in outside logs could be entered into FP registers or abstracted separately. These preliminary data provide valuable information for this K08 proposal, which will comprehensively document screening practices in Mombasa County using all the available documentation sources. We will explore why screening prevalence and appropriate documentation is so low, and address this implementation gap with clinic-specific interventions using SAIA.

E. METHODOLOGY

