4. PROCEDURES

C.2.A. AIM 1: To describe the cervical cancer screening care cascade, from identification of female clients age 21-65 years old, through referral for follow-up of clients with positive or suspicious screens, in FP clinics in Mombasa County. Following characterization of this cascade, we will conduct an analysis of correlates of failure to screen for cervical cancer in FP clients seen over a one-year period.

Study design: This aim will be accomplished by abstracting data from FP registers and interviewing clinic managers. Given the results of the preliminary data presented in C.1.E, any other logs for cervical cancer screening will also be examined to get the most complete and accurate

[figure not shown]

Figure 3. Planned cervical cancer screening care cascade using FP register and other log abstractions

representation of current screening practices. Brief structured interviews with clinic managers will be conducted to understand screening and referral practices in individual FP clinics. Data from FP registers will be merged with clinic-level data from FP clinic manager structured interviews to explore correlates of screening.

Procedures: Cervical cancer screening care cascade: Quantifying the screening care cascade from FP client identification through referrals of positive or suspicious screens will follow a series of steps, illustrated in Figure 4. First, all FP clients 21-65 years of age and recorded at least once during a 3-month period will be identified as a 'cohort' for evaluation over the next 12 months of register data. This step is illustrated taking place retrospectively during the first three months in the figure. Any FP client outside this age range will not be counted as screening is not recommended. The cohort will be followed, using periodic data

[figure not shown]

Figure 4. Family planning register abstraction schema.

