abstraction from the register over the next 12 months. The goal will be to identify whether or not cervical cancer screening was completed within 12 months. Among women with completed screens, we will also determine how many were positive (lesions meeting criteria for dysplasia, or other positive test) or suspicious, and how many of these women were referred for care. To supplement these data, any clinic-based cervical cancer screening logs will also be examined for the same time-period as the FP register abstraction. To understand if FP register documentation is capturing screening, this cascade will be compared with the County DHIS reports, which provide individual clinic level data. The level of correlation between these two sources for total FP clients and total screens will be calculated. While we anticipate using FP registers in Aim 2, we may modify this approach, based on quality and correlation of DHIS and FP register data.

Correlates of screening: Data will be abstracted from the FP registers for individual level information (e.g. number of HIV-positive clients, number of FP commodities dispensed). Brief in-person structured interviews with clinic managers (e.g. staff to patient ratio, manager experience, commodities/resources available in clinic, size of population served, urban/periurban/rural, public vs. public/private partnership) will collect clinic-level characteristics from all included clinics and together, these sources will be used to explore individual- and clinic-level correlates of screening that are expected to be generalizable to all FP clinics in Mombasa County.

Data management: Data abstracted from FP registers, other clinic logs, and structured interview data from clinic managers will be aggregated in a REDCap database (49).

C.2.B. AIM 2: To test whether SAIA increases cervical cancer screening compared to usual procedures in a cluster randomized trial in 20 FP clinics in Mombasa County.

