Screening outside FP clinics: The register abstraction process may not capture whether women have been recently screened. These women would appear to need screening and would be counted as a loss in the cascade. According to the DOH, the most common clinics for cervical screening are FP clinics and HIV clinics, but it is unclear where HIV-positive and HIV-negative women are actually accessing screening. The 2014 estimates (the most recent survey) of screening on the coast of Kenya suggest only 8% of women have ever been screened, which is higher than the 3-month screening prevalence of 0.6% in our preliminary data (C.1.E). Given this estimate, the possibility that a woman had been screened recently is expected to be quite low. Consequently, the vast majority of women require screening. Aim 1 will be used to explore how many clinics are performing any screening, the proportion of women screened, and if screening differs by HIV status. We are focusing on FP clinics, as women attending these clinics are generally expected to be sexually active, at risk for HPV infection, and consequently, cervical cancer. Some HIV-positive women could access screening in HIV clinics. We anticipate quantifying the care cascade separately by client HIV status to better illustrate the landscape of screening practices. Future work could also examine cervical cancer screening in HIV clinics.

Aim 2 Limitations:

New versus all FP clients: If prevalence of screening is found to be very low in Aim 1 (as we expect), the RCT will aim to improve screening for both new and existing FP clients. However, if Aim 1 screening prevalence is higher than expected (we anticipate a cut-off of around 20% screening prevalence), then including existing clients may lead to significant misclassification. In this scenario, Aim 2 will focus on new FP clients only. We anticipate having sufficient power for this alternative approach. Preliminary data suggest an average of 60 new FP clients per clinic in a 3-month period (C.1.E), which we would anticipate would continue throughout a 12-month period. Ten clinics per arm in the RCT with only 60 new clients per clinic would provide at least 80% power to detect a 12% difference between intervention and control arms.

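### The Aim 1 correlates model counts only screening documented at the FP clinic but is read as failure to screen, so its HIV-status odds ratio can be inflated, masked or reversed by screening at HIV clinics

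*Combined protocol and SAP*

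**What the plan says.** Section E.6 (Data management, Aim 1) sets the model: "Cervical cancer screening will be modeled as a binary outcome" and "Logistic regression will be used to examine correlates of screening including age, HIV status of clients, and specific clinic characteristics", with adjustment for clustering by clinic. It has no category for a woman screened elsewhere.

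The outcome source is in E.4 (C.2.A): "This aim will be accomplished by abstracting data from FP registers and interviewing clinic managers". It is extended by: "To supplement these data, any clinic-based cervical cancer screening logs will also be examined for the same time-period as the FP register abstraction". Follow-up covers 12 months of register data. The aim and the title of Table 1 (E.5) both call the outcome failure to screen.

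On other venues, C.1.E reports discussions with the County, "noting that the majority of cervical cancer screening is conducted in either FP clinics or HIV clinics". E.11 (Aim 1 limitations, on screening outside FP clinics) accepts that abstraction may miss recent screens and says: "These women would appear to need screening and would be counted as a loss in the cascade". It adds: "Some HIV-positive women could access screening in HIV clinics". It plans to quantify the cascade separately by HIV status, and then says: "Future work could also examine cervical cancer screening in HIV clinics".

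E.11 (Aim 2 limitations, on identifying women who should be screened) goes further. It treats HIV-negative women as less likely than HIV-positive women to have been screened elsewhere, and offers stratifying by HIV status or excluding HIV-positive women. That offer is made for the trial analysis, not for the Aim 1 model.

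**The concern.** A screen done at a separate HIV clinic is coded as no screen. If that happens more often to HIV-positive women, the outcome error is differential by a covariate whose effect the model is meant to estimate. Neither covariate adjustment nor allowance for clustering removes it. Splitting the cascade by HIV status does not recover the missed screens either, because they stay missed within the HIV-positive group.

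Screening of HIV-positive women is recommended at least annually (section D, A.1), so an HIV-clinic screen would often fall inside the 12-month window. Table 1 plans for HIV-positive status to be more common among women not screened. That is also the direction the register would show if HIV-clinic screening replaced FP-clinic screening.

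Aim 1 could therefore tell the County that HIV-positive women are being missed when some are screened elsewhere. E.11 also relies on Aim 1 to learn where HIV-positive women are screened before settling the Aim 2 population, and the same blind spot weakens that decision.

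**Working it through.** **Step 1. Reproduce Table 1 (E.5).** Inputs: 80% power, alpha 0.05 (taken as two-sided), screened to not screened 1:33. With k = 33, ps and pn the HIV-positive shares in screened and not-screened women, and p̄ = (ps + k·pn)/(1 + k):

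n(screened) = [1.96·√(p̄(1−p̄)(1+1/k)) + 0.842·√(ps(1−ps) + pn(1−pn)/k)]² / (ps − pn)², and total = 34·n.

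- 60% vs 40%: 1655 unrounded, 49 × 34 = 1666 after rounding up; stated 1672.
- 60% vs 20%: 372 unrounded, 11 × 34 = 374 after rounding up; stated 376.

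The sample sizes are sound. The issue is what the outcome measures.

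**Step 2. Turn the planning values into 2×2 tables.**

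| Row | Not screened, HIV+ / HIV− | Screened, HIV+ / HIV− | Recorded OR of failure |
|---|---|---|---|
| 60% vs 40% (1672, 49 screened) | 973.8 / 649.2 | 19.6 / 29.4 | (973.8/19.6)/(649.2/29.4) = 2.25 |
| 60% vs 20% (376, 11 screened) | 219 / 146 | 2.2 / 8.8 | (219/2.2)/(146/8.8) = 6.0 |

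**Step 3. Move missed screens.** Let x be the share of HIV-positive women coded unscreened who were in fact screened at an HIV clinic. The documents give no value, so x is an assumption. Off-site screening in HIV-negative women is first set to zero. The OR for being unscreened anywhere is then:

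| x | 60% vs 40% row | 60% vs 20% row |
|---|---|---|
| 0 | 2.25 | 6.0 |
| 1% | 1.49 | 2.98 |
| 2% | 1.11 | 1.97 |
| 3% | 0.88 | 1.46 |
| 5% | 0.61 | 0.95 |
| 10% | 0.34 | 0.49 |

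The null is reached when the screened proportion in HIV-positive women equals that in HIV-negative women:

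- 60% vs 40%: HIV-negative proportion 29.4/678.6 = 4.33%. Screens needed among 993.4 HIV-positive women: 43.0. Extra: 43.0 − 19.6 = 23.4, so x = 23.4/973.8 = 2.4%.
- 60% vs 20%: 8.8/154.8 = 5.68%. Needed among 221.2: 12.6. Extra: 10.4, so x = 10.4/219 = 4.7%.

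**Step 4. Relax the zero.** If a share y of HIV-negative women coded unscreened were also screened off-site, the 60% vs 40% threshold becomes [(29.4 + 649.2y)/678.6 × 993.4 − 19.6]/973.8, about 2.4% + 0.98y. At y = 1% it is 3.4%. What matters is the difference between the groups.

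**Step 5. Direction.** Take FP-clinic screening of 3% in HIV-negative women, so odds of failure 0.97/0.03 = 32.33. The other rates are assumed.

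| FP-clinic screening, HIV+ | Added HIV-clinic screening | Recorded OR | OR, unscreened anywhere | Effect |
|---|---|---|---|---|
| 3% | 5% | 1.00 | (0.92/0.08)/32.33 = 0.36 | masked |
| 1.5% | 1% | (0.985/0.015)/32.33 = 2.03 | (0.975/0.025)/32.33 = 1.21 | inflated |
| 1.5% | 5% | 2.03 | (0.935/0.065)/32.33 = 0.44 | reversed |

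**The case against.** Several points on the other side stand.

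- **The sponsor saw the problem.** E.11 discloses screening outside FP clinics and splits the cascade by HIV status. It would be wrong to say the issue was overlooked; the gap is that nothing carries through to the Aim 1 model.
- **A recorded odds ratio above 1 needs more than missed screens.** A reader might infer that off-site screening alone will make HIV-positive status look like a correlate of failure. It will not: with equal FP-clinic screening the recorded value is 1.0. Suppose instead that a share q of HIV-positive clients is screened at HIV clinics and never again at the FP clinic, with 3% FP-clinic screening otherwise. Recorded screening is then 0.03(1−q), and matching Table 1's 2.25 needs q of about 55%. The documents support no such figure. Even then, the odds ratio would be right for FP-clinic screening.
- **HIV-clinic use by HIV status is not established.** The documents do not say that only HIV-positive women are screened at HIV clinics, and E.11 says it is unclear where either group goes. They support only that HIV-positive women are likelier to be screened elsewhere.
- **Some HIV-clinic screens may be captured.** E.1 allows an FP clinic to share a facility with other services, including the CCC, and E.4 admits any other screening logs. Only off-site screens are clearly out of reach.
- **Low overall screening.** E.11 cites 8% of coastal women ever screened. That figure covers all women and does not bound HIV-positive women; the thresholds of 2.4% and 4.7% also lie below it.

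The analysis is exploratory, and the randomised comparison does not depend on its coefficients.

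**Conclusion.** The point holds as one of outcome definition and interpretation. As an analysis of screening documented at the FP facility, the model is usable. As an analysis of failure to screen among FP clients, which is how the aim is worded, its HIV-status odds ratio is not interpretable without knowing how much HIV-clinic screening there is.

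At Table 1's planning values, unrecorded HIV-clinic screening in 2.4% to 4.7% of HIV-positive women coded unscreened (about 23 women in 1672, or 10 in 376) moves the true association to null, and more reverses it. This rests on an assumed HIV-clinic screening rate, on no off-site screening in HIV-negative women (the threshold rises almost one for one if there is some), and on planning shares rather than observed data.

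Reversal is possible, not predicted: it requires lower FP-clinic screening in HIV-positive women together with enough HIV-clinic screening. The change is worth making before the Aim 1 analysis because the results go to the County and inform Aim 2.

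**What to change.** In E.6, Aim 1:

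1. Define the outcome as screening documented at the FP facility. Report the HIV-status odds ratio only as a correlate of that, not of being unscreened.
2. Keep all women in the main model. Also fit the correlates model by HIV status (positive, negative, unknown), as E.11 already contemplates for Aim 2.
3. Add a simple bias analysis for the HIV odds ratio over a stated range of HIV-clinic screening, in the manner of the Step 3 table.
4. State that the other logs in E.4 include the screening log of an HIV clinic in the same facility, where one exists, for the same 12 months.

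Dropping HIV-positive women from the main model is not recommended. At the 60% vs 40% planning shares it removes about 993 of 1672 clients and leaves about 679, with 29 screened, whereas the 40% vs 60% facility-level row of Table 1 calls for 1672.

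The cost is a little more analysis and abstraction. Precision within strata will be low. The unknown stratum may be large: C.1.D reports HIV testing for 420 of 4389 new FP clients, though status can be known without a test at that visit. Off-site screens remain unseen, which is why the wording change is needed in any case.

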2. STUDY POPULATION

There will be three different groups of subjects in this research proposal:

1. Individual FP clients' data will be abstracted from FP registers. However, there will be no contact with individual FP clients by study staff.
2. Family planning clinics as a unit to be randomized. Study staff will work with clinic staff for both data abstraction and during the intervention if randomized to this arm of the trial. In addition, micro-costing and time-and-motion studies will be conducted in FP clinics for the SAIA budget impact analysis.
3. Family planning clinic managers and staff.

Inclusion Criteria:

Family planning clinics

Sampling plan: A selection of 20 FP clinics will be selected to be randomized to SAIA versus usual procedures. The FP clinics will receive County-supplied FP products, which generally means they are reporting their activities to the County, including cervical cancer screening. Clinics will be spread out throughout the 5 sub-Counties in Mombasa.

Eligibility: All FP clinics that receive County-supplied FP products will be eligible to participate.

FP clinic managers and staff

Sampling plan: A selection of FP clinic managers and staff will be approached to answer questions about their respective FP clinics in a semi-structured interview. To understand the implementation of cervical cancer screening in the CFIR framework, in-depth interviews will also be conducted with a random sampling of FP clinic managers.

Eligibility: Any FP clinic manager that is 18 years and older is eligible to be interviewed. These clinic managers can be male or female.

FP client data abstraction: Family planning client data will be abstracted from included FP clinics for female FP clients who access FP clinics during our data collection windows. We anticipate including all female FP clients.

Exclusion Criteria

Family planning clinics

Any clinic that is expected to be closed during part or all of the SAIA intervention period will be excluded. Any FP clinic that was previously included in the FP HIV SAIA trial will be excluded.

FP clinic managers and staff

No exclusion criteria

FP client data abstraction: No exclusion criteria.

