Procedures: Quantitative data: Initial information from intervention and control clinics will be obtained from clinic managers. Details about clinic characteristics such as size of the population served and what other services are provided will be collected. Staff characteristics will be collected including the number and type of staff, level of education, and experience of the clinic managers. Cervical cancer screening data will be collected from FP registers including screening method (VIA, visual inspection with Lugol's iodine [VILI], HPV with VILI, HPV alone, Pap smear), clients' HIV status, cervical cancer screening results (positive, negative, suspected), and information on referrals of positive or suspicious screens. These data will be collected at the beginning of the trial during a baseline period before any study procedures are completed, and then periodically every 3 months for all clinics.

Qualitative data: Qualitative IDIs will be conducted with clinic managers to understand cervical cancer screening practices and barriers. Study staff will explain the risks and benefits of participating in the IDIs and the procedures in place to safeguard their opinions. Clinic managers will then be asked to provide written informed consent to participate in an IDI. Types of questions study staff would ask include: "Describe what you know about cervical cancer screening.>"; "In your clinic, what do you think are barriers to screening more women for cervical cancer?"; "What are some ways that cervical cancer screening could be improved in your clinic?". These IDIs will be completed both prior to the trial and during the trial. Questions in the IDIs will be adapted from readily-available CFIR questions to understand where, when, and why the intervention works (50).

Randomization: Restricted randomization will be used to randomize FP clinics into intervention and control arms based on clinic size and location in Mombasa County(51). If facilities differ dramatically in cervical cancer screening rates at baseline, we will also stratify the randomization according to this factor.

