Aim 2: The FP HIV SAIA Trial preliminary results suggest that very little cervical cancer screening is performed or being documented in FP registers. Of these available data, the proportion of FP clients screened was 0.6%. Because this screening prevalence may not be representative, we have used a more liberal estimation of 8% prevalence of screening based on the 2014 DHIS estimates (the most recent resource available). FP clinics had an average of 183 clients in a 3-month period. Most clients follow-up every 3 months so this is a conservative estimate of total clients in a 12-month period. We will assume that following the intervention, 20% of women will be screened for cervical cancer. To calculate a sample size for a cluster RCT, the cluster size variability (κ) must be estimated with literature often citing $\kappa \leq 0.25$ and rarely exceeding 0.5 (54). We have estimated a κ of 0.5 to be conservative, which translates to an intra-class correlation coefficient of approximately 0.05. Cluster size variability of FP clinics was calculated as 0.74 using data in 1.C.E. With an $\alpha=0.05$, 10 clusters per arm will provide 90% power to detect a risk difference of 12% from the intervention.

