7. VARIABLES – DEPENDENT, INDEPENDENT, CONFOUNDERS

Cervical cancer screening care cascade: The care cascade will examine the counts and proportions aggregated from the selected FP clinics. The variables to be abstracted from the FP register includes whether new or return FP client, HIV status, whether cervical cancer screening was conducted, what method of screening was used, what the results were, and if any referrals were made for this screening. This cascade will account for appropriate exits from the cascade (e.g. outside screening age range, or screened negative) and losses in the cascade (e.g. not screened, or positive screen not referred for follow-up).

Correlates of screening: Brief structured interviews with clinic managers as well as FP register data abstraction will collect information on for example, size of the FP clinic, staff, training of staff, age of FP clients, HIV status of clients, availability of FP commodities, level of experience of FP clinic manager, availability of cervical cancer screening commodities, referral practices, and any perceived barriers or facilitators of cervical cancer screening.

Cluster randomized trial: The primary outcome is the proportion of all FP clients aged 21-65 years who were screened for cervical cancer over the total number of eligible clients. These outcomes will be assessed every 3 months in the 12-month study period. We are requesting an additional 6 months for a total RCT study duration of 18 months. In-depth interviews will collect information about implementation of SAIA, barriers and facilitators to screening, and also using consolidated framework for implementation research (CFIR) constructs and domains.

Aim 3: Interviews with clinic managers and clinic observations along with data regarding time and expenses to implement SAIA will be collected. This will include general salary ranges for study staff and clinic staff, commodities needed, time for different clinic procedures, for example.

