Current screening practices vary between FP clinics: It is possible that randomization would select a disproportionate number of clinics in either intervention or control arms that already perform screening. This may bias results. Aim 1 results will be used to decide whether to stratify randomization based on past screening rates.

SAIA interventions not readily identifiable or feasible: Clinic staff may not identify solutions to address bottlenecks. In discussions with [name] (based on his experience with both CQI and the development of SAIA), this can be addressed by highly trained, experienced study staff to guide clinic staff through SAIA. Additionally, other quality improvement tools like root cause analysis and fishbone diagrams can be helpful (57). It is also possible that solutions proposed by staff members may not be feasible. Study staff will help staff to identify solutions that are more feasible in the given context and budget.

Focus on cervical cancer screening: This study will focus on increasing screening and will not address the linkage to treatment for positive screens. While we recognize that referral and treatment are also important, these steps would add complexity to this small study, and we likely would not have sufficient power. In addition, we felt that focusing on screening provided a useful metric for evaluating whether SAIA is potentially effective for addressing cervical cancer prevention. To insure adequate care during the study, we will partner with our Mombasa County collaborators to work programmatically to ensure that women with positive screens are linked to treatment. The extension of SAIA to improve linkage to treatment is a potential aim of a future study.

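### The primary GEE on 20 clinics states no small-sample correction, working correlation or covariates; its ordinary arm-only form has a type I error of about 8–13%, not 5%, unless omitted randomisation factors happen to offset it

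*Combined protocol and SAP*

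**What the plan says.** Section E.6 (Data Management), Aim 2, gives the whole primary analysis: "Generalized estimating equations with a binary link, clustered by clinic, will compare proportions screened in intervention versus control clinics longitudinally". It adds that the purpose is to allow for correlation over time and between clinics, but names no structure.

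Section E.4 (Procedures) says how clinics are allocated: "Restricted randomization will be used to randomize FP clinics into intervention and control arms based on clinic size and location". A further factor is conditional: "If facilities differ dramatically in cervical cancer screening rates at baseline, we will also stratify the randomization according to this factor". Section E.11 repeats the condition: "Aim 1 results will be used to decide whether to stratify randomization based on past screening rates". Section E.7, whose title includes "DEPENDENT, INDEPENDENT, CONFOUNDERS", names no confounder or covariate for the trial. The number of location levels is itself unsettled: the sampling plan in E.2 says "Clinics will be spread out throughout the 5 sub-Counties in Mombasa", while E.1 lists six.

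Section E.5 plans 10 clinics per arm, 8% versus 20% screened, 183 clients per clinic, alpha 0.05 and 90% power. It takes kappa as 0.5, "which translates to an intra-class correlation coefficient of approximately 0.05", and adds: "Cluster size variability of FP clinics was calculated as 0.74 using data in 1.C.E". It does not say which test the power refers to.

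**The concern.** The robust (sandwich) variance of a GEE is justified by a large number of clusters. With 20, it is biased downwards, and a normal reference takes no account of its own sampling error. The ordinary software default therefore tends to give intervals that are too narrow. Unequal clinic sizes make this worse, and so does each clinic-level covariate added without a correction.

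The plan restricts the allocation on clinic-level factors but does not say whether the model contains them. That choice moves the error rate in both directions. At stake is whether the trial's one primary comparison, intended to support wider use of SAIA, has the error rate that the plan claims.

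**Working it through.** **1. The plan's own figures.** With kappa 0.5, the unmatched clinic-level formula is

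c = 1 + (1.96 + 1.2816)² × [p0(1−p0)/m + p1(1−p1)/m + κ²(p0² + p1²)] / (p1 − p0)²

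With p0 = 0.08, p1 = 0.20 and m = 183 (all from E.5), the bracket is 0.0736/183 + 0.16/183 + 0.25 × (0.0064 + 0.04) = 0.0129. So c = 1 + 10.507 × 0.0129/0.0144 = 10.4 per arm. Ten per arm gives 88.7%, or 91.7% without the added 1. ICC 0.05 with equal sizes gives 91.2%. The stated 90% is reproduced within two points.

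Kappa 0.5 corresponds to an ICC of κ²p/(1−p): 0.25 × 0.08/0.92 = 0.022 at 8%, and 0.25 × 0.20/0.80 = 0.0625 at 20%. Over the two arms together it is 0.25 × 0.0464/(0.0736 + 0.16) = 0.0497, so the plan's 0.05 is a fair summary. Under the null at 8% the two readings differ, so both 0.022 and 0.05 were run.

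**2. Type I error by simulation.** The inputs from E.5 are 8% in both arms, 10 clinics per arm and a mean of 183 clients. Assumptions not in the documents:
- two-sided 0.05;
- beta-distributed clinic rates;
- lognormal or gamma clinic sizes, with CV 0 or 0.74 (0.74 is read as the size CV and carried over to the trial clinics);
- predictive strength of the factors: half the between-clinic variance explained by size and location, or a baseline-to-follow-up autocorrelation of 0.5 or 0.8 when stratifying on baseline screening.

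Most cells had 3,000 to 10,000 runs. The ranges cover separately written simulations.

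| Model | Uncorrected sandwich, normal reference | Mancl-DeRouen, t reference, exchangeable |
|---|---|---|
| Arm only, factors not predictive, exchangeable | about 8–10% | about 4–5.5% |
| Same, independence, size CV 0.74 | about 11–13% | n/a |
| Arm only, predictive factors used in allocation but omitted, exchangeable | 4.5–7.7% | 1.8–3.8% |
| Same, independence | 5–12% | n/a |
| One factor added (size, or baseline-screening stratum) | about 8–14% | about 3–5% |
| Size plus two-level location | 12–18% | not reported |
| Sub-county terms with equal clinic sizes (only location acts) | 14–17% | not reported |
| Size plus 5 or 6 sub-counties, size CV 0.74 | 17–25% | about 2–4% |

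The link function (logit, log or identity) moved these figures by only about 0 to 2 points.

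**3. Coverage.** Under the null, coverage is 100% minus the type I error. The nominal 95% interval of the ordinary arm-only form thus covers about 90–92% (exchangeable) or 87–89% (independence, CV 0.74) when the factors are not predictive.

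**4. Repeated quarters.** Four quarters were run with ICC 0.05, size CV 0.74 and stratification on baseline screening. The ordinary exchangeable form gave 7.0% or 4.7% (autocorrelation 0.5 or 0.8) without the stratum and 10.5–11.0% with it. Mancl-DeRouen with t(17) and the stratum gave 4.0–4.2%.

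**5. Low screening rates.** With ICC 0.05, size CV 0.74 and stratification, the adjusted Mancl-DeRouen test gave 5.1–5.9% at a 3% rate and 6.9–7.6% at 1%. A within-stratum permutation test gave 4.8–5.1% and 4.4–5.1%. With kappa 0.5 the corrected GEE held at both rates (3.6–4.2%).

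**6. Power for 8% versus 20%, size CV 0.74.** Under kappa 0.5, arm-only Mancl-DeRouen has 92.0%; stratified and adjusted, 92.7–96.5%. Under ICC 0.05, the arm-only figures are about 91% for the uncorrected test, 83.8% for Mancl-DeRouen and 88.1% for permutation. Stratified and adjusted, Mancl-DeRouen has 86.7–92.4%.

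**The case against.** A reader might infer that the plan commits to an uncorrected test, so that its alpha is certainly inflated. It does not: E.6 is silent, and an analyst could apply a correction and still comply. The criticism is of the default form and of leaving the choice open.

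A reader might also merge all the figures into one range open to any compliant analyst. That goes too far. E.6 compares arms and names no covariate, so its natural reading is unadjusted. The 14–25% arises only if the analyst adds the size and location factors without correction, and adjustment for baseline screening arises only if the conditional stratification takes place.

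Nor do the documents support the inference that the 90% power is wrong; it is reproduced.

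The odd link name carries little weight. Aim 1 uses logistic regression for a binary screening outcome, so logit is the natural reading.

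The ordinary exchangeable test may land near 5% if the allocation factors predict screening and are left out. That stands as a possibility, but the plan gives no information on how strongly they predict.

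An unweighted clinic-level t-test is simpler and gives 4–5.5% when the factors are not predictive. It is a legitimate alternative, but it gives up the longitudinal GEE that the plan chose and drops to 2–3.5% when predictive factors are ignored.

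The checks have limits. Most cells use one period, the 18-month (six-quarter) duration was not run, and the permutation test was checked only within baseline-screening strata, not over allocations restricted on size and location.

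**Conclusion.** The concern holds in this form: with 20 clinics, the ordinary reading of E.6 does not deliver the stated 0.05. The arm-only excess is about 3 to 5 points with exchangeable correlation and 6 to 8 points with independence and size CV 0.74, provided the randomisation factors do not predict screening. If they do and are omitted, the exchangeable form moves towards 5%. That is an offset whose size rests on assumed predictive strength, not a safeguard, and it disappears once the factors enter the model uncorrected.

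The result depends on the 8% rate, on a size CV of 0.74 applying to the 20 trial clinics where that figure is used, and on the simulation assumptions listed. Absence of detail is judged on the public text. This should be fixed before analysis; the design need not change.

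**What to change.** In Section E.6, name one primary test:
- binomial GEE, logit link, exchangeable working correlation within clinic;
- terms for arm and quarter, plus at most one or two terms for factors actually used in the randomisation (the baseline-screening stratum if used, one term for size), and no term per sub-county;
- Mancl-DeRouen covariance;
- t reference with 18 df less the number of clinic-level covariates.

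Report a permutation test over the allocations that the restricted randomisation allowed, as a prespecified sensitivity analysis. This reflects location without spending model terms. Make it primary only under a rule fixed in advance, such as a pooled baseline screening rate below a stated level, because the corrected GEE can still reject too often when screening is rare. In Section E.5, state which test the 90% power refers to.

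The cost is a few sentences, plus saving the list of admissible allocations at randomisation. The critical value rises from 1.96 to 2.10 on 18 df, 2.11 on 17 or 2.12 on 16, so the interval widens. The corrected test is slightly conservative at 8%, and more so if predictive factors are left out. The sponsor should state openly the power loss under ICC 0.05 with an arm-only model; the higher figure belongs to a test that does not hold its level.
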